4.1 Screened Population

Approximately 300 males and females will be screened from participating STD clinics, emergency departments or ambulatory clinics in different regions of the US.

4.2 Eligible Population

This population includes screened participants who meet all inclusion/exclusion criteria in the protocol. The criteria are

- Inclusion Criteria: Subjects must meet all the following inclusion criteria to be eligible to participate in the study:
 - 18 years of age or older
 - Be able to provide informed consent
 - Report having a history of allergy to PCN or B-lactam drugs
- Exclusion Criteria: Subjects meeting any of the following criteria at baseline will be excluded from study participation:
 - Not able to stay for testing and challenge (1-3 hours) on day of clinic visit (or return within 2 weeks to complete study procedures)
 - Other exclusion criteria, per clinical judgment, which prohibits enrolling in study

4.3 Enrolled Population

This population includes all eligible participants who consent to enroll in the study. This analysis population will mainly be used for analyzing participants' baseline characteristics and allergy history.

4.4 Treated Population

This population includes all enrolled participants who received Method 1 PST or Method 2 DOC. This analysis population will mainly be used for analyzing participants' baseline characteristics, primary outcome measures and secondary outcome measures.

4.5 Per-Protocol Population

This population includes all treated participants who completed the study without protocol deviation. This analysis population will also be used for analyzing participants' baseline characteristics, primary outcome measures and secondary outcome measures.

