6.3.1 One-step Oral Challenge (PST Group)

After confirming the participant is qualified, amoxicillin 250 mg will be administered, and time of administration will be recorded. The subjects will be observed for 60 minutes \pm 10 minutes, after which vital signs, the PE and peak flow will be repeated. Note that each observation time point has a time window of +/- 10 minutes.

If subjects report the presence of difficulty breathing, swelling in lip/mouth/tongue/throat, eye itchiness/tearing, skin hives/itchiness or abdominal pain/nausea/vomiting while they are waiting for final evaluation, study staff will include the reactions with the post-oral challenge vital signs and the focused PE assessment performed after the 60-minute observation period \pm 10 minutes. Standard treatment will be provided, including antihistamines, steroids and/or epinephrine, if indicated and dependent on the specific medical condition that arises.

If vital signs (including peak flow) and focused PE are within reasonable limits after the 60-minute \pm 10 minutes waiting period, the subject will be counseled that they do not have an allergy to PCN (B-lactams). They will be provided with written documentation that they will be encouraged to share with their medical providers, including the STD clinic and their primary care physician (if they have one).

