6.3.2 Two-step Direct Oral Challenge (DOC Group)

Preliminary Dose

After confirming the participant is qualified, amoxicillin 25 mg will be administered, and time of administration will be recorded. The subjects will be observed for 30 minutes \pm 10 minutes, after which vital signs including peak flow will be repeated.

Administration of Full Challenge Dose

If vital signs are within reasonable limits after the 30-minute \pm 10 minutes waiting period, the subject will be given the full challenge dose of 250 mg amoxicillin. The subject will be observed for an additional 30 minutes \pm 10 minutes, after which vital signs, the PE and peak flow will be repeated.

If subjects report the presence of difficulty breathing, swelling in lip/mouth/tongue/throat, eye itchiness/tearing, skin hives/itchiness or abdominal pain/nausea/vomiting while they are waiting for final evaluation, study staff will include the reactions with the post-oral challenge vital signs and the focused PE assessment performed after 30-minute \pm 10 minutes observation period. Standard treatment will be provided, including antihistamines, steroids and/or epinephrine, if indicated and dependent on the specific medical condition that arises.

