6.6.4 Protocol Deviations

A protocol deviation (PD) is any noncompliance with the study protocol, GCP or protocol-specific Manual of Procedures requirements. The noncompliance may be either on the part of the participant, the SI, or other study personnel. As a result of deviations, corrective actions will be developed through a plan agreed upon by the site, the study Principal Investigator and DMID and then implemented promptly.

It is the responsibility of the SI and other study personnel to use continuous vigilance to identify and report deviations within five working days of identification of the PD, or within five working days of the scheduled protocol-required activity. All deviations must be promptly reported to DMID using the approved DMID PD form and reporting methods.

All deviations from the protocol must be addressed in study participant source documents. A completed copy of the DMID PD form must be maintained in the Regulatory File. PDs must be sent to the local IRB/Independent Ethics Committee per their guidelines. The SIs and other study personnel are responsible for knowing and adhering to their IRB requirements.

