7.1.2 Post-Skin Testing

- Subjects will be observed for 30 + 5 minutes and 60 + 5 minutes after skin testing. Assessment of elicited reactivity to PCN will include local skin reactions including erythema, induration and itching which will be evaluated both by self-report and physical exam. Systemic reactions are extremely rare.
- Subjects with positive skin tests will not progress to oral challenge step.

An impending generalized reaction to immediate hypersensitivity skin testing is unusual. If any acute reactions occur, they will be treated as necessary and reported to the IRB and DMID as required.

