7.3 Analysis of Primary Objective

The primary analysis will be performed on the Treated population and Per Protocol population. Estimates with corresponding exact (Clopper-Pearson) 95% confidence intervals for the following measures will be provided:

- The prevalence of PCN reactivity validated either by skin test or by direct oral challenge among those participants who report a history of PCN (B lactam) allergy and who have low-risk histories.
- The NPV on true PCN (B-lactam) allergy of the algorithm / PCN (B-lactam) allergy history screening questionnaire performance in the Treated population.

The NPV for each low-risk allergy item listed on the questionnaire will be estimated and will be compared with the prevalence of PCN reactivity using exact test of binomial proportion. The p-values will be adjusted with Benjamini-Hochberg procedure.

To construct a short standardized post-study questionnaire (4-6 questions) from the PCN (B-lactam) allergy history screening questionnaire, we will first use the item-characteristic curve from Item Response Theory (IRT) to evaluate each question item's discrimination ability of true PCN (B-lactam) allergy and use variable importance evaluation functions to indicate which questions are most useful for predicting the true PCN (B-lactam) allergy. Based on the results of IRT and variable importance analyses, we will then apply machine learning approaches such as random forest (Svetnik et al., 2003) via R package caret, to select a short post-study questionnaire that has the highest NPV among those possible short questionnaires with 4-6 selected questions.

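### The Per-Protocol set, one of two sets used for the primary analysis, drops participants for any protocol deviation, however trivial; with few reactors this can move the NPV in either direction

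*SAP*

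**What the plan says.** SAP 4.5 admits to the Per-Protocol set only those who finished free of deviations: "This population includes all treated participants who completed the study without protocol deviation". It does not distinguish major from minor deviations, or those that bear on the test result from those that do not.

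The breadth of the rule comes from Protocol 6.6.4: "A protocol deviation (PD) is any noncompliance with the study protocol, GCP or protocol-specific Manual of Procedures requirements". The source of the lapse does not matter: "The noncompliance may be either on the part of the participant, the SI, or other study personnel".

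On use, SAP 7.3 opens with "The primary analysis will be performed on the Treated population and Per Protocol population". Its NPV bullet then refers to "questionnaire performance in the Treated population". SAP 4.4 lists the primary outcome measures among the main uses of the Treated set, and SAP 4.5 adds the Per-Protocol set for the same measures. No sentence says which result governs if the two differ.

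The SAP does not define study completion. By design, some reactors stop early. Protocol 7.1.2 says "Subjects with positive skin tests will not progress to oral challenge step". In the DOC Group (Protocol 6.3.2), the step at which "the subject will be given the full challenge dose of 250 mg amoxicillin" is conditional on acceptable vital signs after the first dose.

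**The concern.** Read together, SAP 4.5 and Protocol 6.6.4 discard a valid test result for reasons unrelated to it, such as a consent-filing error or a late form. If such losses are unrelated to reacting, the cost is only precision.

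They may not be unrelated, because reactors and non-reactors go through different procedures. Reactors in the oral challenge need treatment and extra recording while the timed assessments are still due ("Note that each observation time point has a time window of +/- 10 minutes"). Skin-test reactors never reach those timed steps. In addition, if completion is read as finishing every procedure, participants who correctly stop at a positive result leave the set by definition.

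The primary outcome rests on very few reactors, so a small imbalance in who is dropped can shift the NPV and its exact lower bound. If the two sets then give different messages, the plan does not say which one counts.

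**Working it through.** **1. The plan's own figure.** SAP section 6 gives sensitivity 85%, specificity 95%, prevalence 3% and an estimated NPV of 99.51%.

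NPV = 0.95×0.97 / (0.95×0.97 + 0.15×0.03) = 0.9215 / 0.9260 = 99.51%, as stated.

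The stated sample size also reproduces. The log-odds formula for a lower bound of 98.4%, 85% power and a one-sided 5% level gives 938.8. Dividing by 0.95 for the 5% with a high-risk history gives 988.2, against 988 in the plan. This is background only, because the point does not depend on it.

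**2. Expected reactors.** The 1,000 evaluable participants less 5% high-risk leave 950 tested. 950 × (1 − 0.9951) = 4.7, or about 5. Base case: 5/950, NPV 99.47%, two-sided exact (Clopper-Pearson) lower bound 98.78%. One reactor is worth 1/950 = 0.105 percentage point.

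**3. Effect of exclusions.** Let x be the reactors among n treated, d1 the share of reactors dropped and d0 the share of non-reactors dropped. Then

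expected Per-Protocol NPV = 1 − x(1−d1) / [x(1−d1) + (n−x)(1−d0)].

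The change from the Treated NPV has the sign of d1 − d0. The documents give neither rate, so every value of d0 and d1 below is an assumption. The 28-reactor case (about 3% of 950) is also an assumption.

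| Reactors of 950 | d0 | d1 | Expected NPV |
|---|---|---|---|
| 5 | none dropped | none dropped | 99.47% |
| 5 | 20% | 20% | 99.47% |
| 5 | 10% | 40% | 99.65% |
| 5 | 10% | 0% | 99.42% |
| 28 | none dropped | none dropped | 97.05% |
| 28 | 10% | 40% | 98.02% |
| 28 | 10% | 0% | 96.74% |

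Exact lower bounds for the 5-reactor rows, with counts rounded to whole participants: 98.78% (5/950), 98.66% (4/760), 98.98% (3/853) and 98.64% (5/855). The 20%/20% row shows pure loss of precision: the estimate is unchanged and the bound falls from 98.78% to 98.66%.

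**4. Can it change the reading against 98.4%?** Yes, both ways. The reactor counts here are assumed, and 10% of non-reactors are dropped in each case.

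- 8/950 has lower bound 98.35%, below 98.4%. Dropping 2 of the 8 reactors leaves 942×0.9 ≈ 848 non-reactors and 6 reactors: 6/854, lower bound 98.48%, above it.
- 7/950 has lower bound 98.49%, above 98.4%. Dropping no reactors leaves 943×0.9 ≈ 849 non-reactors and 7 reactors: 7/856, lower bound 98.32%, below it.

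**The case against.** A reader might infer that reactors are more exposed to deviations, so that the Per-Protocol NPV is pushed upward. The documents do not support that. They give no deviation rates and do not link deviations to reacting. Skin-test positives skip the oral challenge and its time windows. A DOC participant who does not receive the second dose because of the first is following the protocol, and treating a reaction is specified procedure. Extra recording for challenge reactors could work the other way, but nothing in the text settles the balance.

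Two apparent examples of harmful exclusion are in fact proper ones. A higher-risk participant tested in error does not belong in an NPV for low-risk histories. A missing post-challenge assessment means that the negative result was never established.

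A reader might also infer that the two sets have equal standing. That goes too far. The NPV bullet names the Treated set, the Per-Protocol set is introduced as a further one, and the Treated estimate is reported whatever happens to the other. The analysis sections describe estimates with exact intervals and attach no success rule to either set; 98.4% is a planning bound. SAP section 4 also requires reasons for exclusion to be documented, and the Per-Protocol flow diagram (SAP Figure 2), which is not visible in the text reviewed, might narrow the rule.

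These arguments limit the consequence. They leave three gaps in the visible text: the unrestricted exclusion rule, the missing ranking and the undefined completion. Documenting reasons afterwards neither narrows the rule nor keeps the decision independent of the result.

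**Conclusion.** The point holds as a defect of definition and ranking. As written, SAP 4.5 removes treated participants for deviations that cannot affect the test result, and SAP 7.3 carries the resulting set into the primary analysis without saying which set governs. The certain cost is precision. Bias is possible in either direction, and its sign cannot be determined from the documents.

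The size is small in absolute terms: about 0.1 percentage point of NPV per reactor lost at the planned scale. That is enough to carry the exact lower bound across 98.4% in either direction when the Treated result lies close to it. The figures rest on 950 tested participants, about 5 reactors under the planned NPV, and assumed deviation rates. The Treated analysis remains intact and is reported alongside, so the consequence is limited to interpretation of the second set.

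**What to change.** In SAP 4.5, limit Per-Protocol exclusions to a short prespecified list of deviations that can change the risk classification or the reference result. Examples are a higher-risk participant tested in error, a wrong reagent or dose given, a test not read or a post-challenge assessment missing, and disqualifying medication. Decide each case from a deviation listing that omits the test result.

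State that a participant who stops because of a positive skin test or a challenge reaction has completed the study.

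In SAP 7.3, name the Treated set as primary and the Per-Protocol set as a sensitivity analysis, and tabulate Per-Protocol exclusions by reactor status.

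The cost is SAP wording plus the preparation and review of one masked deviation listing. The listing needs a separate extract, because the skin-test and challenge forms carry the results themselves. No new data are collected.

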4.6 Provider Population

The Provider Population includes all clinic providers who complete the provider feasibility survey. This analysis population will mainly be used for analyzing secondary outcome measures for provider acceptability and feasibility of PCN allergy evaluation including the allergy history screening questionnaire, skin testing and oral challenge in busy ambulatory STD settings.

5. GENERAL STATISTICAL ISSUES

All confidence intervals will be two-sided with 95% coverage. Likewise, all statistical tests will be two-sided and at 0.05 significance level.

Missing data will be treated as missing at random without imputation unless available evidence indicated that missing data is informative. Data at all non-missing time points will be used and included in relevant analyses.

All comparisons between treatment groups will be made without adjustment for multiple comparisons. All statistical analyses will be done using SAS® (SAS Institute Inc., Cary) Version 9.4.

6. Sample Size Consideration

The sample size for this study was selected to have adequate study power to conclude a high NPV of the PCN (B-lactam) allergy history screening questionnaire in ruling out the presence of true PCN (B-lactam) allergy. The approach proposed by Steinberg et al. (2009) is used to obtain the minimal sample size needed to achieve a lower 95% confidence bound for NPV that exceeds the result with a useless test at a fixed level of significance with a given study power. To target at least 85% power at 5% of significant level, the listed sample sizes (see table) provide lower 95% confidence bounds for NPV under the following various assumptions:

- The true population prevalence with PCN allergy: 1%, 3%, 5%
- The observed % of PCN allergy in this study: 1%, 3%, 5%
- The PCN allergy diagnostic kit with sensitivity at least 85% and specificity 95%
- 5% of participants who report a PCN allergy history will have a high-risk allergy history and therefore will not proceed to skin testing.

Population prevalence of PCN allergy	Observed % of PCN allergy in study	Estimate d NPV	The lower 95% confidence bound for NPV						
			99.0%	98.4 %	97.9 %	97.5 %	97.3 %	97.0 %	95.0 %
1%	1%	99.84%	1259	796	635	556	526	488	351
	3%	99.51%	420	265	212	185	175	163	117
	5%	99.18%	252	159	127	111	105	98	70
3%	1%	99.84%	8119	2964	1958	1559	1421	1259	759
	3%	99.51%	2707	988	653	520	474	420	253
	5%	99.18%	1624	593	392	312	284	252	152
5%	1%	99.84%	11600	9519	4770	3378	2950	2483	1259
	3%	99.51%	37547	3174	1590	1126	984	828	420

	5%	99.18%	22533	1905	954	676	590	497	252
--	----	--------	-------	------	-----	-----	-----	-----	-----

A sample of 988 subjects who reported to have PCN allergy history would provide an estimated NPV = 99.51% with 85% power to conclude that the NPV of the study allergy history screening questionnaire is least 98.4% at 5% significant level.

7. STATISTICAL ANALYSIS

7.1 Study Participant Disposition and Follow-up

Information about study participant disposition and follow-up during the study will be provided and summarized for each treatment group as follows:

- A flowchart will document the flow of participants through the study and relate this to the different analysis populations. See Appendix A.
- Tables will summarize:
 - the number and percentage of participants included in each of the analysis populations, excluded, with high-risk history of PCN allergy, who received skin testing, who received oral challenge and who completed the study.
 - the reasons for early discontinuation from the study including the number who refused to participate in skin testing, the number who refused oral challenge etc.

7.2 Analysis of Baseline Data

Baseline variables will be summarized for the Treated population, the Enrolled population and the Per Protocol Population. The following baseline measures collected at the screening and enrolment visits from participants will be summarized by treatment group:

- Demographic data: age, gender, ethnicity and race.
- Allergy history
- Vital signs and focused physical exam

For PST Group only:

- HIV status, last CD4 (within last 6 months) and HAART status if HIV+
- Skin conditions
- Skin testing history

For DOC Group only:

- Current pregnancy status of female participants (assigned female at birth)

The following pre-trial survey results of providers will be summarized by site:

- Practice setting
- Type of provider
- Specialty or defined area of practice

- Current approach to penicillin (PCN) allergic patients
- Access to PCN skin testing and whether PCN skin testing/oral challenge is offered.
- Barriers to offering/performing PCN skin test/oral challenge

Data will be presented in summary tables by treatment group, site and overall. Categorical variables, and continuous variables that have been categorized at discrete levels, will be summarized by frequencies and percentages. Continuous variables will be summarized in means, standard deviations, medians, minima and maxima.

7.3 Analysis of Primary Objective

The primary analysis will be performed on the Treated population and Per Protocol population. Estimates with corresponding exact (Clopper-Pearson) 95% confidence intervals for the following measures will be provided:

- The prevalence of PCN reactivity validated either by skin test or by direct oral challenge among those participants who report a history of PCN (B lactam) allergy and who have low-risk histories.
- The NPV on true PCN (B-lactam) allergy of the algorithm / PCN (B-lactam) allergy history screening questionnaire performance in the Treated population.

The NPV for each low-risk allergy item listed on the questionnaire will be estimated and will be compared with the prevalence of PCN reactivity using exact test of binomial proportion. The p-values will be adjusted with Benjamini-Hochberg procedure.

To construct a short standardized post-study questionnaire (4-6 questions) from the PCN (B-lactam) allergy history screening questionnaire, we will first use the item-characteristic curve from Item Response Theory (IRT) to evaluate each question item's discrimination ability of true PCN (B-lactam) allergy and use variable importance evaluation functions to indicate which questions are most useful for predicting the true PCN (B-lactam) allergy. Based on the results of IRT and variable importance analyses, we will then apply machine learning approaches such as random forest (Svetnik et al., 2003) via R package caret, to select a short post-study questionnaire that has the highest NPV among those possible short questionnaires with 4-6 selected questions.

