8.2 Sample Size Considerations

The sample size for this study was selected to have adequate study power to conclude a high NPV of the PCN (B-lactam) allergy history screening questionnaire in ruling out the presence of true PCN (B-lactam) allergy. To address the objective properly, we applied Steinberg's et al.³² approach to obtain the minimal sample size needed to achieve a lower 95% confidence bound for NPV that exceeds the NPV with a useless test at a fixed level of significance with a given study power. Based on this approach, the sample size calculation depends on the prevalence of PCN allergy in the population and among observed study participants and the sensitivity and specificity of the PCN allergy diagnostic kit (PRE-PEN®). To target at least 85% power at 5% of significant level, the listed sample sizes (see table) provide lower 95% confidence bounds for NPV under the following various assumptions:

- The true population prevalence with PCN allergy: 1%, 3%, 5%
- The observed % of PCN allergy in this study: 1%, 3%, 5%
- The PCN allergy diagnostic kit with sensitivity at least 85% and specificity 95%
- 5% of participants who report a PCN allergy history will have a high-risk allergy history and therefore will not proceed to skin testing.

Population prevalence of PCN allergy	Observed % of PCN allergy in study	Estimated NPV	The lower 95% confidence bound for NPV						
			99.0%	98.4%	97.9%	97.5%	97.3%	97.0%	95.0%
1%	1%	99.84%	1259	796	635	556	526	488	351
	3%	99.51%	420	265	212	185	175	163	117
	5%	99.18%	252	159	127	111	105	98	70
3%	1%	99.84%	8119	2964	1958	1559	1421	1259	759
	3%	99.51%	2707	988	653	520	474	420	253
	5%	99.18%	1624	593	392	312	284	252	152
5%	1%	99.84%	113000	9519	4770	3378	2950	2483	1259
	3%	99.51%	37547	3174	1590	1126	984	828	420

	5%	99.18%	22533	1905	954	676	590	497	252
--	----	--------	-------	------	-----	-----	-----	-----	-----

For example, with 3% PCN allergy prevalence in population and among observed study participants, the NPV for a useless test is 97%. A useful PCN (B-lactam) allergy history screening questionnaire should have the lower 95% confidence bound for NPV greater than 97%. Based on the list a minimum sample size of 988 subjects who reported to have PCN allergy history would provide an estimated NPV = 99.51% with 85% power to conclude that the NPV of the study allergy history screening questionnaire is least 98.4% at 5% significant level.

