2.1 Primary Objective

- Validate an algorithm which incorporates a PCN (B-lactam) allergy history screening questionnaire followed by an allergy validation intervention — 1) skin testing and oral challenge or 2) direct two-step oral challenge — to produce a short standardized post-study questionnaire (4-6 questions) for use in ambulatory STD settings.
- Determine how many subjects who report PCN (B-lactam) allergy can be treated with PCN or B-lactam drugs.

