3. STUDY OUTCOME MEASURES

3.1 Primary Outcome Measures

- Algorithm / PCN (B-lactam) allergy history screening questionnaire performance in ambulatory STD populations, specifically the negative predictive value (NPV) of the algorithm on true PCN (B-lactam) allergy.
- In ambulatory STD patients who report a history of PCN (B lactam) allergy and who have low-risk histories, determine the prevalence of PCN reactivity validated either by skin test or by direct oral challenge.

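### The primary NPV is worded for an algorithm that contains its own reference standard, and the 99.51% and N = 988 behind it describe the skin-test kit rather than the questionnaire

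*SAP*

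**What the plan says.** The primary objective (Protocol 3.1.1, SAP 2.1) is to "Validate an algorithm which incorporates a PCN (B-lactam) allergy history screening questionnaire followed by an allergy validation intervention", meaning either skin test plus challenge or a direct two-step challenge. The first primary outcome (Protocol 3.2.1 and 8.1.1, SAP 3.1) opens with algorithm and questionnaire joined by a slash, then narrows to "specifically the negative predictive value (NPV) of the algorithm on true PCN (B-lactam) allergy". The primary analysis keeps the slash: Protocol 8.4.1, and SAP 7.3, which estimates "The NPV on true PCN (B-lactam) allergy of the algorithm / PCN (B-lactam) allergy history screening questionnaire performance in the Treated population".

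The sample-size text names only the questionnaire. Protocol 8.2 seeks "adequate study power to conclude a high NPV of the PCN (B-lactam) allergy history screening questionnaire", and SAP 6 says the same. The accuracy put into that calculation belongs to another test: "The PCN allergy diagnostic kit with sensitivity at least 85% and specificity 95" per cent. Protocol 8.2 also sets the benchmark: "with 3% PCN allergy prevalence in population and among observed study participants, the NPV for a useless test is 97" per cent. A useful questionnaire should have a lower 95% bound above that, and the worked example aims for a bound of 98.4%.

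Only low-risk subjects go on to skin test or challenge (Protocol 6.1.2.2 and 6.2). The Treated population is those who received either method (SAP 4.4). No section gives a two-by-two table, says which result counts as test-negative, or defines true allergy separately from the skin test and challenge.

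**The concern.** An NPV needs a test, a negative result, a reference standard and a denominator. Here the test has two names, and the choice changes who counts.

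- **Questionnaire.** Every low-risk subject is a negative, and every later reactor is a failure.
- **Complete algorithm.** The negatives are those who passed the challenge, which is also the reference. No failure is possible in either group.
- **The sample-size calculation.** It has the arithmetic of a third test, the kit. There a skin-test positive leaves the denominator, and only allergy that the kit missed is a failure.

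The product of the trial is a short history form of four to six questions. If the index test is not fixed before analysis, a figure that describes the kit or the challenge could stand as the primary NPV, set against a benchmark that the questionnaire itself would not be expected to clear.

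**Working it through.** **Inputs.** Protocol 8.2: prevalence 3% in the population and in the study, kit Se = 0.85 and Sp = 0.95, 5% high-risk and not tested, target lower bound 98.4%, power 85%, alpha 5%. SAP 1: 1,000 evaluable. SAP 7.3: exact (Clopper-Pearson) intervals. Tested: 1,000 × 0.95 = 950.

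**1. The plan's NPV.** Sp(1−p) / [Sp(1−p) + (1−Se)p] = 0.95×0.97 / (0.95×0.97 + 0.15×0.03) = 0.9215 / 0.9260 = 99.51%. This matches Protocol 8.2 and uses only the kit's accuracy.

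**2. The plan's N.**
- φ1 = (1−Se)/Sp = 0.15/0.95 = 0.1579.
- φ0 = (0.016/0.984) × (0.97/0.03) = 0.5257.
- [ln(φ0/φ1)]² = 1.447.
- Variance term: Se/[(1−Se)×0.03] + (1−Sp)/[Sp×0.97] = 188.94.
- (z0.95 + z0.85)² = 7.189, with one-sided alpha.
- n = 7.189 × 188.94 / 1.447 = 938.8 tested, and 938.8/0.95 = 988.2 enrolled.

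This reproduces 988. The same formula gives all 63 cells of the Protocol table within 3%. So 99.51%, 988 and 85% power all describe an 85%/95% test.

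**3. The questionnaire in the Treated population.** Everyone there is questionnaire-negative, so NPV = 1 − prevalence of reactivity, the other primary outcome. Against true allergy at 3%, 950 × 0.03 = 28.5. Taking 28 failures, 922/950 = 97.05%, exact 95% CI 95.8 to 98.0 (29 failures give 96.95%). The lower bound exceeds 97% only with 18 or fewer reactors (1.9%), and 98.4% only with 7 or fewer (0.7%). At a true 3% the chances are about 2% and about 0%.

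**4. Kit accuracy applied to all 950.** Kit-negative: 0.926 × 950 ≈ 880. Missed: 0.0045 × 950 ≈ 4. NPV = 876/880 = 99.5%, exact 95% CI 98.8 to 99.9. The chance that the lower bound exceeds 98.4% is about 86%.

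**5. Complete algorithm.** 922 of 922 = 100% by construction.

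**6. Matched prevalence rows, 950 tested.**

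| Prevalence (population and study) | Useless-test value | Questionnaire NPV (lower bound) | Kit accuracy NPV (lower bound) |
|---|---|---|---|
| 1% | 99% | 98.9% (98.1%) | 99.9% (99.4%) |
| 3% | 97% | 97.05% (95.8%) | 99.5% (98.8%) |
| 5% | 95% | 94.9% (93.4%) | 99.2% (98.3%) |

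Failures are rounded to whole subjects: 10, 28 and 48 in 950 for the questionnaire; 1 in 895, 4 in 880 and 7 in 864 for the kit. In each row the questionnaire's lower bound is below the useless-test value and the kit's is above it.

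**The case against.** The best reply is that the questionnaire was meant all along. The slash is already in the outcome definition, so it reads as a loose synonym. The skin test and challenge are presented as ways to validate allergy, that is, as the reference. Protocol 2.2.6 wants a high NPV from the instrument, and the analysis sections plan an NPV for each question or item, which suits only a questionnaire. All of this stands, and it settles which way to fix the text. It does not remove the literal reference to the NPV of the algorithm, nor the kit-based calculation. Nor can 85%/95% be read as the questionnaire's own accuracy: that would make 0.03×0.85 + 0.97×0.05 = 7.4% questionnaire-positive, against the stated 5% high-risk.

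A reader might infer more than the documents support.

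- **A gap of up to 8 points.** In the PST group alone (475 tested), counting the kit's 5% false positives gives 37 failures in 475, NPV 92.2%. That changes the reference from true allergy to observed reactivity and drops the DOC half. With 14 DOC failures added it is 51 in 950, 94.6%. With true allergy held as the reference, the gap is about 2.5 points.
- **Opposite answers everywhere.** They occur on matched rows, not in every cell. At 1% observed allergy against a 97% benchmark both readings pass, since the questionnaire's lower bound is 98.1%, though it still misses 98.4%.
- **A planned skin-test endpoint.** No section proposes questionnaire plus negative skin test as the primary index test, and it could not apply to the DOC group. Nothing says that the overall NPV will be reported as the short form's. SAP 7.3 plans estimation with exact intervals and sets no pass/fail test of the overall NPV; the 97% criterion is in Protocol 8.2 only.

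**Conclusion.** The point holds. As worded, the primary NPV belongs to an algorithm that includes its own reference standard, while the precision promised for the questionnaire is that of the kit. On the plan's 3% case with 950 tested, the questionnaire's NPV against true allergy is about 97.0% (95.8 to 98.0), against about 99.5% (98.8 to 99.9) at kit accuracy.

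This rests on three assumptions. First, the 3% applies to tested, low-risk subjects, as the division by 0.95 implies. If it applied to all reporters, and the 5% high-risk had 12% to 17% true allergy (my assumption, taken from the skin-test rates for urticaria and anaphylaxis in Protocol 2.1), low-risk prevalence would be (0.03 − 0.05×0.12)/0.95 = 2.5% to (0.03 − 0.05×0.17)/0.95 = 2.3%. The NPV would be 97.5% to 97.7%, with about 24 to 21 reactors, still above the 18 that the 97% limit allows. Second, skin test plus challenge identifies true allergy without error. Third, all 950 complete testing. The 99.5% is for comparison only, because the kit is used in the PST group alone.

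**What to change.** 1. In Protocol 3.2.1, 8.1.1 and 8.4.1 and SAP 3.1 and 7.3, replace both 'algorithm /' and the later reference to the algorithm's NPV with the NPV of the questionnaire's low-risk classification. Deleting the slash alone would leave the second reference in place.
2. State that every skin-test positive and every challenge positive is a failure and stays in the denominator, and that this NPV equals one minus the prevalence of reactivity in the Treated population.
3. State how the analysis handles skin-test negatives who were never challenged, such as pregnant subjects (Protocol 5.3) and those who decline (Protocol 6.3).
4. Report the NPV of low-risk history plus negative skin test against the challenge only as a separate, labelled PST-group estimate among challenged subjects. Report no NPV for the complete algorithm.
5. In Protocol 8.2 and SAP 6, state that 99.51%, 988 and 85% power describe a test with the kit's accuracy, and give the questionnaire's expected NPV and precision: about 97.0% (95.8 to 98.0) at 3% with 950 tested. Add that kit false positives counted as failures would lower the observed figure.

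The cost is wording and one table row. The headline NPV becomes less favourable, and the two primary outcomes become complements of each other, which the SAP should say openly.
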